## **2. GENERAL ANALYSIS DEFINITIONS**

All types of analysis together with the description of rules for handling missing or incomplete data are described later in this document. These analyses will include vaccinated participants with respect to the actual vaccine administered (ie, Groups 1, 2, 3, 4, 5 and 6). Also, participants who receive only the first

vaccination (Ad26.ZEBOV or placebo) will be included in accordance with the randomization group with that first vaccination. Otherwise, the participant will be excluded from summary tables and graphs but will be included in listings. For instance, a participant who will receive MVA-BN-Filo as Dose 1 will not be included in summary tables and graphs.

In general, the study data will be analyzed as follows:

- Categorical variables will be summarized with a frequency table presenting counts and percentages.
- Continuous variables will be summarized using the following statistics, as appropriate: number of observations, arithmetic mean, geometric mean, corresponding 95% CI, standard deviation, median, quartiles (Q1 and Q3), minimum, and maximum.

*Baseline value* will be defined as the value of the last available assessment performed prior to the first vaccination (Dose 1) on Day 1, unless specified otherwise.

For safety assessments, the *baseline value* will be an assessment performed prior to or on the date (if only time of assessment is missing) of the first vaccination. The *baseline value* for immunogenicity assessments will be an assessment performed before or on the date of the first vaccination. In case of multiple values, the value closest to the vaccination will be used as the *baseline value*.

*Visit day* will be determined relative to the actual day of vaccination (ie, date of Dose 1 or Dose 2).

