Descriptive statistics (including geometric means with their corresponding 95% CIs, median, interquartile range, minimum, maximum, as applicable) will be calculated for continuous immunologic parameters at each time point. Graphical representations of immunologic parameters will be prepared, as applicable. Frequency tabulations will be calculated for discrete (qualitative) immunologic parameters at each time point.

To assess the primary objective, each pairwise comparison (ie, Groups 1 vs 2, 1 vs 3, 2 vs 3) of the anti-EBOV GP binding antibody responses 21 days post Dose 2 vaccination with MVA-BN-Filo will be based on ratios of the GMCs with corresponding 95% CI. Equivalence of any 2 groups will be shown if the

95% CI of the estimated GMC ratio lies entirely within 0.5 and 2.0. Lot-to-lot consistency is accomplished if equivalence is shown for all 3 pairwise comparisons.

For the secondary objective, each pairwise comparison of the anti-EBOV GP binding antibody responses 56 days post Dose 1 vaccination with Ad26.ZEBOV will be based on ratios of the GMCs with corresponding 95% CI. Equivalence of any 2 groups will be shown if the 95% CI of the estimated GMC ratio lies entirely within 0.5 and 2.0. Lot-to-lot consistency (for Ad26.ZEBOV) is accomplished if equivalence is shown for all 3 pairwise comparisons.

As a sensitivity analyses, both the primary and secondary hypotheses of equivalence will also be tested based on data of participants who received the second vaccination within the original window (± 3 days) around the Day 57 visit.

Safety Analyses

No formal statistical testing of safety data is planned. All the participants who received at least 1 dose of the study vaccine will be included in the safety analysis. The reporting of the categorical safety data will include the incidence, severity, relatedness, and type of adverse events. Continuous safety parameters will be descriptively analyzed (showing the mean, standard deviation, median and quartiles [Q1 and Q3]).

Baseline for all vital signs and physical examinations will be defined as the last evaluation done before Dose 1 vaccination.

TIME AND EVENTS SCHEDULE

	Screening/Baseline ^a	Vaccination and Postvaccination Visits ^b					Follow-up Day 237^r (Telephone call for safety follow-up) ±15d
	Day 1	Day 29 (Telephone call for safety follow-up) ±1w	Day 57 Groups 1-4: -3d, +28d (Day 54-85)^u Groups 5 and 6: ±1w	Day 78 ±3d	Day 85 (Telephone call for safety follow-up) ±1w		

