11.1. Analysis Sets

Full Analysis Set: The full analysis set will include all participants with at least one study vaccine administration documented. Participants will be analyzed according to the study vaccine they actually received.

Per Protocol Analysis Set: The per protocol analysis set will include all randomized and vaccinated participants, who received both Dose 1 and Dose 2 vaccinations (administered within the protocol-defined window), had at least one postvaccination (ie, after the date of vaccination) evaluable immunogenicity sample, and had no major protocol deviations that may influence the immune response. The per protocol analysis set will be defined for participants included in the immunogenicity subset. Similarly, the per protocol analysis set for the Booster Cohort (Groups 5-6) will include all vaccinated participants, who received Dose 1, Dose 2, and the booster vaccination (ie, both Dose 2 and Ad26.ZEBOV booster vaccination within the protocol-defined window), had at least one postvaccination (ie, after the date of vaccination) evaluable immunogenicity sample, and had no major protocol deviations that may influence the immune response.

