11.4. Safety Analysis

No formal statistical testing of safety data is planned. All the participants who received at least 1 dose of the study vaccine will be included in the full analysis set. The reporting of the categorical safety data will include the incidence, severity, relatedness, and type of adverse events. Continuous safety parameters will be analyzed descriptively (showing the mean, standard deviation, median, and quartiles [Q1 and Q3]).

Baseline for all vital signs and physical examinations will be defined as the last evaluation done before Dose 1 vaccination.

Adverse Events (Including Reactogenicity)

The verbatim terms used in the eCRF by investigators to identify adverse events will be coded using the Medical Dictionary for Regulatory Activities (MedDRA). For each adverse event, the percentage of participants who experience at least 1 occurrence of the given event will be summarized by group. In addition, comparisons between groups will be provided if appropriate. All reported adverse events and events-related diary information (solicited local at injection site and systemic, and unsolicited) with onset within 28 days post Dose 1, Dose 2 or booster dose vaccination (ie, treatment-emergent adverse events) will be included in the analysis. For each adverse event, the number and percentage of participants who experience at least 1 occurrence of the given event will be summarized by vaccination group.

Summaries, listings, datasets, or participant narratives may be provided, as appropriate, for those participants who die, who discontinue study vaccine due to an adverse event, or who experience a severe or a serious adverse event.

Solicited local (at injection site) and systemic adverse events will be summarized descriptively. The overall frequencies per vaccine group as well as frequencies according to severity and duration will be calculated for solicited adverse events. In addition, the number and percentages of participants with at least one solicited local (at injection site) or systemic adverse event will be presented. Frequencies of unsolicited adverse events, separately for all and vaccination-related only, will be presented by System Organ Class and preferred term, while those of solicited adverse events will be presented only by preferred term.

Vital Signs

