## 2.3. Analysis Sets

Vaccination assignment will follow the “as treated” principle. That is, participants will be analyzed according to the actual vaccine received.

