### 2.3.1. Full Analysis Set

The full analysis set will include all participants with at least one study vaccine administration documented.

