### 4.1. Demographics and Baseline Characteristics

Demographic and screening/baseline characteristics will be tabulated and summarized with descriptive statistics per vaccination group (as shown in Table 2) and over all participants. The following demographic and baseline characteristics will be summarized:

- Sex (Female/Male)
- Age (years)
- Race
- Ethnicity
- Height (cm)
- Weight (kg)
- Body mass index (BMI, kg/m^2), calculated from the recording of baseline height and weight
- Baseline EBOV-GP binding antibody (EU/mL) positivity, only for the immunogenicity subset and the booster cohort
- Positivity of baseline viral neutralizing antibody (VNA) against the Ad26 vector (IC90 titers), only for the booster cohort

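### SAP section 2 keeps a dosed participant with a wrong-product sequence out of the safety tables, although the plan puts everyone dosed in the safety analysis

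*SAP*

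**What the plan says.** SAP section 2 sets general rules and introduces them as covering all types of analysis. Two kinds of vaccinated participant are included: those whose vaccine as given corresponds to one of Groups 1 to 6, and those who had only a first dose, of Ad26.ZEBOV or placebo. The rule for the rest is: "Otherwise, the participant will be excluded from summary tables and graphs but will be included in listings". The SAP gives an example: "a participant who will receive MVA-BN-Filo as Dose 1 will not be included in summary tables and graphs".

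The safety population is described elsewhere without any condition on sequence:

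- Protocol synopsis, Safety Analyses: "All the participants who received at least 1 dose of the study vaccine will be included in the safety analysis".
- Protocol 11.4: "All the participants who received at least 1 dose of the study vaccine will be included in the full analysis set".
- SAP 2.3.1: "The full analysis set will include all participants with at least one study vaccine administration documented".
- SAP 5 performs the safety analyses on that full analysis set.

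Protocol 11.1 and SAP 2.3 add the as-treated principle; in the SAP's words, "participants will be analyzed according to the actual vaccine received".

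On layout, SAP 5 presents safety data by the groups of Table 2, with denominators taken within a group. SAP 5.2 summarises vital signs per group. Neither mentions an overall column. By contrast, SAP 4.1 says that demographics "will be tabulated and summarized with descriptive statistics per vaccination group (as shown in Table 2) and over all participants", and SAP 4.2 also plans an overall disposition column.

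SAP 2.3.2 has a separate rule for a wrong batch: such participants are left out of the primary and secondary hypothesis tests only. That rule is one of the considerations for the per protocol immunogenicity analysis.

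**The concern.** A participant given the wrong product has been exposed to study vaccine and is in the full analysis set by definition. Under section 2 that person is nonetheless counted in no adverse event table, in neither numerator nor denominator. The safety tables would then rest on fewer people than the set they are said to be based on, and those missing would be people with dosing errors, whose safety data a reader would want to see. SAP 1.6 lists two changes to the planned analyses, one on the make-up of the immunogenicity subset and one on physical examination findings. This exclusion is not among them, so nothing tells the programmer or the reader which instruction governs.

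**Working it through.** The plan states no figure here to reproduce. The check is a comparison of texts, followed by simple proportions for scale.

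**Step 1. Does the exclusion reach safety?** Section 2 covers all types of analysis and names tables and graphs without restricting them to immunogenicity. SAP 5 contains no override. So it does.

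**Step 2. Does it reach people who are in the full analysis set?** Membership needs one documented dose. MVA-BN-Filo given first is a documented dose. The SAP's own example is therefore in the full analysis set and out of the tables.

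**Step 3. Which sequences are caught?**

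| Sequence received | Section 2 | Other text | Result |
|---|---|---|---|
| First dose only, Ad26.ZEBOV or placebo | Kept | Full analysis set | Consistent |
| MVA-BN-Filo as Dose 1 | Excluded, by the SAP's example | Full analysis set | Conflict |
| Active product mixed with placebo | Fits no group, so excluded | Full analysis set | Conflict |
| Right products, unpaired lots (for example Lot A, then Lot 2) | Fits no Table 2 group if read literally | SAP 2.3.2: out of the hypothesis tests only | Unclear for safety |

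The last row cannot be settled from the text. SAP 2.3.2 points to a narrow exclusion for lot errors, but it does so within per protocol immunogenicity and is silent on safety tables.

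**Step 4. Does appearing in listings satisfy the protocol's promise?** SAP 5.1.2 builds the adverse event analysis on the number and percentage of participants with events, and SAP 5 takes the denominators from the analysis set within a group. A person absent from both counts is not in that analysis.

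**Step 5. Size.** The documents give no count of unmatched sequences, so k is an assumption. The planned number in Groups 1 to 4 is 3 × 234 + 39 = 741. The share removed from the safety tables is k / 741:

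- k = 1: 1 / 741 = 0.13%
- k = 3: 3 / 741 = 0.40%
- k = 5: 5 / 741 = 0.67%

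For one person set against a single group, the share is 1 / 234 = 0.43% of an active group or 1 / 39 = 2.56% of the placebo group.

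**The case against.** The strongest reply is that section 2 governs display, not membership. Nobody is removed from the full analysis set, listings are a planned safety output, and protocol section 11 leaves specific details to the SAP. It is true that membership is untouched. But the planned safety analysis consists essentially of tables, so the distinction does not meet the synopsis statement or SAP 5. Removing dosed people from those tables also goes beyond filling in detail.

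The second reply is that the event is unlikely and the information survives. Much of this stands:

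- The interactive web response system assigns the matching kit, unblinded qualified staff prepare doses, and an independent monitor oversees the pharmacy.
- Section 2 keeps the participant in listings, SAP 5.1.1 lists all collected unsolicited events, and SAP 5.1.2 provides listings and/or narratives for serious events and for vaccine misallocation.
- A wrong-product dose would presumably also appear in the major deviation summary and listing of SAP 4.4.
- No formal safety testing is planned.

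These facts limit the consequence; they do not remove the contradiction.

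The third reply is that such a person belongs to no Table 2 group and that placing them in one would misattribute events. That is right. It argues for a separate column, a total or a footnote, not for silence.

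A reader might infer that safety data would be lost or serious events hidden. The documents do not support that, given the listings and narratives. A reader might also infer that every lot mix-up is dropped from the safety tables; SAP 2.3.2 makes that doubtful.

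**Conclusion.** The contradiction is real for wrong-product sequences. SAP section 2 excludes them from the safety tables, while the protocol synopsis, SAP 2.3.1 and SAP 5 include them, and SAP 1.6 is silent. For mixed-lot sequences the finding is only that their place in the safety tables is unclear. For demographics and disposition, the overall summaries in SAP 4.1 and 4.2 need only be reconciled with section 2.

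Severity is minor. The effect arises only if such a participant occurs. The documents report none, and each would account for about 0.13% of the 741 planned. It would be wrong to infer any effect on the lot-consistency conclusion: the primary test uses the per protocol set and does not depend on how safety tables are filled.

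**What to change.** Amend the SAP wording as follows.

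1. In section 2, confine the catch-all exclusion to immunogenicity tables and graphs.
2. In section 5, state that the safety tables include all full analysis set participants as treated, and that a participant whose products fit none of Groups 1 to 6 is shown under *Other sequence* or counted in an overall total.
3. State that participants with lot mix-ups remain in the active-vaccine safety tables, and give the rule that assigns them to a group.
4. Say that the overall summaries in SAP 4.1 and 4.2 include all these participants.

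If the sponsor prefers to keep the exclusion, declare it in SAP 1.6, footnote the number excluded under each safety table, and say whether the overall summaries in SAP 4.1 and 4.2 count these people.

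The cost is a few sentences and at most one extra column or total in the safety tables. No new data are needed.

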**Table 1: Study Objectives and Endpoints**

Objectives	Endpoints
Primary	
 
• To demonstrate that the paired 2-dose vaccine regimens from 3 consecutively manufactured lots of Ad26.ZEBOV as Dose 1 and 3 consecutively manufactured lots of MVA-BN-Filo as Dose 2, administered at a 56-day interval, induce an equivalent humoral immune response.
 
• Binding antibody levels against the EBOV GP using enzyme-linked immunosorbent assay (ELISA, ELISA units/mL [EU/mL]) at 21 days post Dose 2 vaccination.
 

Secondary	
 
• To demonstrate that 3 consecutively manufactured lots of Ad26.ZEBOV as Dose 1 induce an equivalent humoral immune response.
 
• Binding antibody levels against the EBOV GP using ELISA (EU/mL) at 56 days post Dose 1 vaccination.
 
• To assess the safety and reactogenicity of a heterologous 2-dose vaccine regimen of Ad26.ZEBOV and MVA-BN-Filo administered intramuscularly (IM) on Days 1 and 57, respectively, using 3 different lots of Ad26.ZEBOV and 3 different lots of MVA-BN-Filo. 
 
• Solicited local and systemic adverse events until 7 days post each vaccination.
 
• Unsolicited adverse events until 28 days post each vaccination.
 
• Serious adverse events until the end of the study.
 
 
 

Exploratory (Booster Cohort only)	
 
• To assess the humoral immune response to a booster dose of Ad26.ZEBOV given 4 months after Dose 2 
 
• Binding antibody levels against the EBOV GP using ELISA (EU/mL) at pre booster (Day 177) and several post booster timepoints (7-days, 21-days, 6-months and 12-months post booster dose)
 
 
 

 
To assess the safety and reactogenicity of a booster dose of Ad26.ZEBOV
 
	
 
Solicited local and systemic adverse events until 7 days post booster vaccination.
 
Unsolicited adverse events until 28 days post booster vaccination.
 
Serious adverse events until the end of the study.
 

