Depending on the extent of the COVID-19 impact on the study, additional participants will be recruited in the immunogenicity subset. For instance, shortly after participants received Dose 1 vaccination, “stay-at-home” orders were imposed in the areas where the sites were located. Although the sites had implemented appropriate safety measures to prevent spread of SARS-CoV-2, approximately 22% of participants did not return to the site within the original protocol-defined windows ( $\pm 3$  days) for Dose 2 administration. Investigators were then instructed to bring participants back to the site to complete the vaccine regimen, even if they were out of window. Currently, the “stay-at-home” orders have been lifted and some

participants are returning to the sites for follow-up. In order to reduce the number of additional participants needed for the primary and secondary immunogenicity analyses without jeopardizing the evaluation of the primary and secondary objectives of the study, the window around Dose 2 administration for the main part of the study (Groups 1-4) was widened in CTP Amendment 3. In particular, the upper limit of the window around Day 57 (Dose 2) was extended to Day 85 (ie, Day 57+28 days). The widening of window was deemed acceptable after examination of the immunogenicity data from previous studies (ie, VAC52150EBL2001 and VAC52150EBL2002) in which Dose 2 was administered at intervals  $\geq$ 56 days. Although there appears to be a trend of increasing GMCs with increasing intervals between Dose 1 and Dose 2 from those studies, the variability (standard deviation) of the immune responses (binding antibody levels against the EBOV GP using ELISA [EU/mL]) remains stable and in line with the currently assumed standard deviation of 0.55 (on the log10-scale). Assuming that the delayed Dose 2 administration will be randomly distributed among the groups (ie, Groups 1-4), widening the acceptable time frame to administer Dose 2 by increasing the upper limit of the window to 28 days (ie, Day 57+28 days) is not expected to adversely affect the primary and secondary objectives of the study. See CTP Amendment 3 for further details. Unless otherwise mentioned in this document, the “protocol-defined window” refers to the visit windows as defined in CTP Amendment 3.

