## 2.1. Analysis Periods/Phases

Because the analysis of adverse events (AEs) will be presented per period (and not per time point), these will be assigned to the analysis periods based on [Table 3](#).

For the analysis that will be presented by time point (eg, immunogenicity data), the electronic case report form (eCRF) visit schedules will be used for the post baseline assessments as follows:

- For the analysis based on the per protocol set, only assessments that fall within the protocol-defined visit window will be used.
- For other analyses based on the full analysis set (if applicable), the assessments that fall outside the protocol-defined windows will also be included. If only unscheduled visits are present for a time point, then the one closest to the scheduled visit will be used. If distances of multiple assessments to the scheduled visit are equal, the measurement with the latest date will be used.

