**Table 3: Analysis Period Definitions**

Phase	Period	Interval	
		From	To
Screening		Date and time of signing the informed consent form	One minute prior to start of post-dose 1 period
Regimen	Post-dose 1	Date and time of first vaccination	Minimum of: 
 
a) 23:59 on the date of last contact (for early discontinuation)
 
b) 23:59 on the date of database cut-off date in case of primary (or interim) analysis
 
c) 23:59 of 28 days after the first vaccination (23:59 of day of vaccination + 28 days)
 
d) One minute prior to post-dose 2 period
 

Phase	Period	Interval	
		From	To
Post-dose 1 FU		One minute after post-dose 1 period ends	Minimum of: a) 23:59 on the date of last contact (for early discontinuation) b) 23:59 on the date of database cut-off date in case of primary (or interim) analysis c) One minute prior to post-dose 2 period
Regimen	Post-dose 2	Date and time of second vaccination	Minimum of: a) 23:59 on the date of last contact (for early discontinuation) b) 23:59 on the date of database cut-off in case of primary (or interim) analysis c) 23:59 of 28 days after the second vaccination (23:59 of day of vaccination + 28 days)
Post-dose 2 FU		One minute after post-dose 2 period ends	Minimum of: a) 23:59 on the date of last contact (for early discontinuation) b) 23:59 on the date of database cut-off in case of primary (or interim) analysis c) 23:59 on the date of last study visit d) One minute prior to post-dose 3 period
Regimen	Post-dose 3	Date and time of third vaccination	Minimum of: a) 23:59 on the date of last contact (for early discontinuation) b) 23:59 on the date of database cut-off in case of interim analysis c) 23:59 of 28 days after the third vaccination (23:59 of day of vaccination + 28 days)
Post-dose 3 FU		One minute after post-dose 3 period ends	Minimum of: a) 23:59 on the date of last contact (for early discontinuation) b) 23:59 on the date of database cut-off in case of primary (or interim) analysis c) 23:59 on the date of last study visit

FU: Follow-up

Note: Dose 3 corresponds to booster vaccination.

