### 2.3.2. Per Protocol Analysis Set

The per protocol analysis set for the main part of the study (Groups 1-4) will include all randomized and vaccinated participants, who received both Dose 1 and Dose 2 vaccinations (administered within the protocol-defined window), had at least one postvaccination (ie, after the date of vaccination) evaluable immunogenicity sample, and had no major protocol deviations that may influence the immune response. Similarly, the per protocol analysis set for the Booster Cohort (Groups 5-6) will include all vaccinated participants, who received Dose 1, Dose 2, and the booster vaccination (ie, both Dose 2 and booster vaccination within the protocol-defined window), had at least one postvaccination (ie, after the date of vaccination) evaluable immunogenicity sample, and had no major protocol deviations that may influence the immune response.

Note that the per protocol analysis set will only be defined for participants included in the immunogenicity subset and the booster cohort. The following will be considered for the immunogenicity analysis based on the per protocol analysis set:

- The primary and secondary hypotheses will be based on those in the set with data at 21 days post Dose 2 and 56 days post Dose 1, respectively. Participants who will receive incorrect batch (other than the one randomized to) of vaccination will only be excluded from these hypothesis tests.
- Immunogenicity samples obtained after missed doses (or out-of-window Dose 2 or Dose 3 vaccinations), samples obtained after natural infection (if applicable), or samples obtained outside the protocol-defined window will be excluded in graphs and tables showing descriptive statistics. These measurements will however be shown in listings, together with the indication that they are not used in the analysis.
- If more than 10% of participants from the full analysis set are excluded from the per protocol analysis set, then the immunogenicity analysis (including both primary and secondary hypothesis testing) will be repeated on the full analysis set to evaluate the robustness of the analysis results.

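### Does the SAP's visit-day definition, which omits the booster date, put on-time post-booster samples at risk of exclusion?

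*SAP*

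**What the plan says.** SAP section 2 covers all six groups and states that visit day "will be determined relative to the actual day of vaccination (ie, date of Dose 1 or Dose 2". The booster is not listed.

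Inclusion of samples is handled elsewhere. For data shown by time point, SAP 2.1 says "the electronic case report form (eCRF) visit schedules will be used for the post baseline assessments as follows", and for the per-protocol set "only assessments that fall within the protocol-defined visit window will be used". SAP 2.3.2 adds that "samples obtained outside the protocol-defined window will be excluded in graphs and tables showing descriptive statistics"; the excluded values remain in listings. SAP 1.2 explains that the protocol-defined window "refers to the visit windows as defined in CTP Amendment 3", unless the SAP says otherwise.

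The booster appears in several other places. The note to SAP Table 3 says "Dose 3 corresponds to booster vaccination". SAP 2.3.2 deals with samples taken after "out-of-window Dose 2 or Dose 3 vaccinations". SAP Table 1 sets the exploratory endpoint before the booster and at "several post booster timepoints (7-days, 21-days, 6-months and 12-months post booster dose").

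The protocol's Time and Events Schedule for Groups 5-6 gives the booster as Day 177 ±1 week. The visits that follow are Day 184 ±2 days, Day 198 ±3 days, Day 357 ±2 weeks and Day 537 ±4 weeks, each labelled by its distance from the booster. Protocol 6.1 and 9.1.1 count visits after a postponed Dose 2 or booster from the day the dose was actually given.

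**The concern.** The abbreviation in the parenthesis makes the list exhaustive, so read strictly a post-booster sample has no anchor except Dose 1 or Dose 2. The booster may move by a week either way, while the next two visits are allowed only 2 and 3 days. With an earlier anchor, a participant boosted on Day 183 and sampled exactly 7 days later, on Day 190, would miss Day 184 ±2.

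The two listed anchors can also disagree. If that participant had Dose 2 on Day 63, Day 190 is 127 days after Dose 2, which is the nominal gap (184 − 57 = 127), so the sample would be in window.

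Because per-protocol tables and graphs drop out-of-window samples, correctly timed results could disappear from the summaries of a group of about 50. The choice of anchor would then decide which ones.

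**Working it through.** **Schedule.** The nominal days reproduce: 57 + 120 = 177 (booster), 177 + 7 = 184, 177 + 21 = 198, 177 + 180 = 357, 177 + 360 = 537.

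**Literal reading.** Let the booster be given *b* days from nominal, *b* = −7 to +7 (15 whole days, Days 170 to 184). A sample taken exactly on time after the booster is also shifted by *b*. It falls outside a fixed window of half-width *w* when |*b*| > *w*.

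| Visit | Fixed window | On-time sample falls on | Booster days that lose it |
|---|---|---|---|
| 7 days | 182–186 (*w* = 2) | 177–191 | 170–174, 180–184: 10 of 15 |
| 21 days | 195–201 (*w* = 3) | 191–205 | 170–173, 181–184: 8 of 15 |
| 6 months | 343–371 (*w* = 14) | 350–364 | 0 of 15 |
| 12 months | 509–565 (*w* = 28) | 530–544 | 0 of 15 |

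If the protocol's postponement clauses are taken to cover every late booster, only early boosters remain: 5 of 15 (Days 170–174) and 4 of 15 (Days 170–173).

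**Booster anchor.** A sample 7 ± 2 or 21 ± 3 days after the actual booster is in window by construction, so 0 of 15 booster days lose an on-time sample.

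**Which reading do the documents support?**

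1. The inclusion rules in SAP 2.1 and 2.3.2 do not use the term visit day. They refer to the eCRF visit schedule and to the protocol's windows. No sentence makes the section 2 parenthesis the test of whether a sample is in window.
2. The imported windows belong to visits named 7 days, 21 days, 6 months and 12 months after the booster, and the endpoint in SAP Table 1 is named the same way. Counting a 7-day post-booster result from Dose 1 would contradict its own definition. For example, a sample on Day 186 after a Day 170 booster would pass as a 7-day result at 186 − 170 = 16 days.
3. The printed study days are nominal. In Groups 1-4, Dose 2 may be given as late as 57 + 28 = Day 85. The 21-day visit would then fall on 85 + 21 = Day 106, whereas Day 78 + 3 is only Day 81. The schedule works only if a post-dose visit is counted from the dose it follows.
4. Section 2 states that same principle, the actual day of vaccination. Only its list of examples stops short, while Table 3 and section 2.3.2 do carry the third dose.

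**The case for a change.** The best case for a change is that likely intent is not a written rule. No SAP sentence names the booster as the anchor for data shown by time point. The protocol clauses that do so are worded for a postponed dose, and 6.1 concerns illness or fever, so an early booster on Days 170–176 is not expressly covered. The full-analysis-set repeat in SAP 2.3.2 would not reliably catch the problem: it is triggered when more than 10% of participants are excluded from the per-protocol set, not when single samples are dropped for timing. A participant can stay in the set on one evaluable sample and still lose the 7-day value. The remedy would be a few words.

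The textual points stand: the list is incomplete, and the postponement clauses do not reach every in-window shift. What is missing is the link to harm. The loss needs an analyst to carry a parenthesis from section 2 into inclusion rules that point elsewhere, and then to apply it against the name of the endpoint.

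The counts do not supply that link. They give every possible day equal weight, and the documents contain no distribution of booster or Dose 2 dates, so they cannot be read as an expected proportion.

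**Conclusion.** This is a clerical slip: a parenthesis not brought up to date for the booster. The arithmetic of the literal reading is right, but that reading is not the one the plan's inclusion rules call for. With windows counted from the actual booster date, no on-time sample is excluded and no result is expected to change.

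Even under the literal reading, the reach is small. It would touch only the exploratory 7-day and 21-day descriptive summaries in Groups 5-6 (about 50 active and 10 placebo participants). There is no hypothesis test on the booster, excluded values would still be listed, and the equivalence tests in Groups 1-3 would be unaffected.

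The conclusion assumes that the eCRF visit schedule follows the protocol's visit labels, and that the analysts time each post-dose visit from the dose it follows, as the same schedule already requires for Dose 2. On that basis no change to the plan follows.
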